Appendix 4: Additional Methodology Details

Details of Bayesian analysis of posterior distributions of the SDAI scores

Notations/Definitions

$i = 1, 2, \dots, n$; where n is the total number of patients

x_i^B = Baseline SDAI score for Patient i

x_i^W = Week W SDAI score for Patient i

$y_i = -(x_i^W - x_i^B)$; negative change from baseline SDAI at Week W for Patient i

$I_i^D = \begin{cases} 1, & \text{if Patient } i \text{ received Treatment } D \\ 0, & \text{otherwise.} \end{cases}$

[figure not shown]
$d1, d2, d3$: Dose levels of IRAK – 4

P = Placebo treated group

Primary Model – Bayesian Analysis of Covariance

$$y_i = \mu_P^* I_i^P + \sum_{j=1}^3 (\mu_P^* + \Delta_j^*) I_i^{dj} + \beta(x_i^B - \mu^B) + \varepsilon_i,$$

where $\varepsilon_i \sim N(0, \sigma_\varepsilon^2)$

Data visualization techniques

Table shells of figures displaying the primary endpoint results (see below) will be provided in programming document.

- Distribution of treatment effect *for each* Δ_j^* .
- Display of change from baseline by treatment group based on Bayesian Analysis of Covariance.
- Display of change from baseline by treatment group based on Bayesian Analysis of Covariance vs baseline SDAI.

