After an up to 28 day screening period, eligible subjects in regions where tofacitinib's inclusion as an active control is accepted by local regulatory authorities and ethics committees will be randomized in to receive 1 of 4 dose regimens of PF-06650833 (400 mg, 200 mg, 60 mg, 20 mg MR tablets QD), tofacitinib 5 mg BID, or placebo (matching MR tablets for PF-06650833 QD and matching tofacitinib tablets BID) in a 6 : 6 : 6 : 5 : 5 : 5 ratio in a blinded fashion (Figure 2). In order to maintain the blind and minimize bias, all subjects will receive the same number and types of tablets each day. Subjects assigned to PF-06650833 will all take 4 MR tablets, consisting of a mixture of active PF-06650833 and/or matching placebo tablets dispensed in a blister pack, once per day. In countries in which regulatory authorities and ethics committees accept the use of tofacitinib as an active control in this trial, subjects also will take 1 matching tofacitinib placebo tablet (dispensed in bottles) BID. Subjects assigned to receive tofacitinib will take 1 tablet (dispensed in bottles) of tofacitinib citrate (5 mg) BID. These subjects will also take 4 MR tablets of placebo matching PF-06650833 MR tablets (dispensed in a blister pack) once daily (Table 5). In regions where tofacitinib's inclusion in this study as an active control is not accepted by local regulatory authorities and ethics committees, subjects will only be randomized to PF-06650833 or matching placebo (dispensed in blister packs) and will not receive bottles of tofacitinib or matching placebo (Table 6).

Figure 2. Study Design Schematic

[figure not shown]

Table 5. Dosing and Administration of Investigational Products in Regions Where the Use of Tofacitinib in This Study is Acceptable to Regulatory Authorities and Ethics Committees

Treatment group (n)	Treatment PF-06650833 or matching placebo (packaging)	Tofacitinib or matching Placebo (Packaging)	Total number tablets per day
PF-06650833 400 mg, QD n=36	4 x100 mg PF-06650833 tablets, QD, (Blister Pack)	1 tofacitinib matching placebo, BID, (Bottle)	6
PF-06650833 200 mg, QD n=36	2 x 100 mg PF-06650833 + 2 x PF-06650833 placebo tablets, QD, (Blister Pack)	1 tofacitinib matching placebo, BID, (Bottle)	6
PF-06650833 60 mg, QD n=36	3 x 20 mg PF-06650833 + 1 PF-06650833 placebo tablets, QD, (Blister Pack)	1 tofacitinib matching placebo, BID, (Bottle)	6

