9.2. Efficacy Analysis

Analysis of the Primary Endpoint Primary efficacy analysis will be conducted on SDAI change from baseline at 12 weeks.

Analysis will include data on all PF-06650833 arms and placebo. Data on the 5 mg tofacitinib arm will not be included in the analysis.

The primary analysis will be conducted on intention-to-treat population, defined as all randomized patients who received at least one dose of investigational drug or a placebo. The sensitivity data sets will be outlined in the SAP and will include per-protocol data set.

The primary analysis will assess the posterior distribution of the placebo adjusted SDAI Week 12 changes from baseline for each of four active arms estimated from a Bayesian ANCOVA model adjusting for baseline SDAI score. Placebo adjusted distribution of active arm is defined as distribution of the difference of two random variables: SDAI 12w change from baseline of the given active arm and the placebo (each of them assessed using Bayesian ANCOVA which is equivalent of having treatment indicator as nominal variable in the

model). The sensitivity analysis will include a model with baseline SDAI and TNF exposure as covariates. The distribution means and variances will be reported. Grid plots visualizing the distributions will be presented. The sensitivity analysis will also include models assuming beta-binomial and negative binomial distributions for SDAI score. The same covariate structure will be employed.

The secondary analyses will include pairwise comparison of the four active PF-06650833 arms and the placebo using the ANCOVA models of the same structure. No prior knowledge on placebo will be integrated. The raw and adjusted for multiplicity p-values will be reported. (Multiplicity adjustment will be performed using Hochberg's test). Means and variances of placebo adjusted treatment effects will be reported.

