5.1. Hypotheses and Decision Rules

For any given active arm, the null hypothesis that the distributions of SDAI change from baseline at Week 12 are the same for the active and the placebo arms will be tested using Bayesian framework outlined in the [Appendix 4](#). The separation from the placebo will be judged based on the probability of the posterior distribution of the treatment effect (Δ^*) being greater than zero.

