6. ANALYSES AND SUMMARIES

6.1. Primary Endpoint(s)

The primary efficacy analysis will be conducted on SDAI change from baseline at Week 12. Analysis will include data on PF-06650833 (400, 200, 60, 20 mg, QD) and placebo arms.

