6.1.1. Primary Analysis

The primary analysis will be based on the Bayesian analysis outlined in [Appendix 4](#). The Bayesian analysis will be based on ITT population set.

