7. INTERIM ANALYSES

At least one interim analysis (IA) for futility may be performed. The final number and timing of the IA(s) will be defined by the sponsor, but preliminarily one may be conducted at approximately 6 months after the randomization of the first subject and/or after at least 50% of the planned subjects, ie, approximately 100 subjects, completed the twelve week active treatment phase.

The futility analysis of SDAI change from baseline at Week 12 will be utilizing the Bayesian framework outlined in [Appendix 4](#). Noninformative prior distribution model for the placebo arm, outlined in [Appendix 4](#), will be used for the interim analysis data. The futility might be declared if the posterior probability of the treatment effect being greater than zero is less than 10% for all the active arms.

The interim analysis will not have an option to stop the trial early for efficacy.

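### The primary Bayesian ANCOVA in SAP Appendix 4 has terms for three PF-06650833 doses, but four are randomised, so as printed one unnamed dose has no primary posterior

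*SAP*

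**What the plan says.** Protocol 3 randomises subjects to "receive 1 of 4 dose regimens of PF-06650833 (400 mg, 200 mg, 60 mg, 20 mg MR tablets QD"), or to tofacitinib or placebo. Protocol 9.2 leaves tofacitinib out of the efficacy analysis and asks for a posterior distribution of the placebo-adjusted Week 12 SDAI change "for each of four active arms estimated from a Bayesian ANCOVA model adjusting for baseline SDAI score".

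SAP 6.1 agrees on the arms: "Analysis will include data on PF-06650833 (400, 200, 60, 20 mg, QD) and placebo arms". SAP 6.1.1 then hands the model to Appendix 4: "The primary analysis will be based on the Bayesian analysis outlined in" that appendix.

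Appendix 4 defines "d1, d2, d3$: Dose levels of IRAK"-4 and gives the primary model as

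y_i = μ_P* I_i^P + Σ_{j=1..3} (μ_P* + Δ_j*) I_i^{dj} + β(x_i^B − μ^B) + ε_i,

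where y_i is the negative of the SDAI change, so a positive Δ_j* favours the drug. It also plans a figure of the treatment-effect distribution for each Δ_j*.

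Two rules take their input from this model. SAP 5.1 says of any given active arm: "The separation from the placebo will be judged based on the probability of the posterior distribution of the treatment effect" exceeding zero. SAP 7 says that futility might be declared if that probability is "less than 10% for all the active arms", using a "Noninformative prior distribution model for the placebo arm".

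**The concern.** Three treatment terms cannot give four posteriors. Because d1 to d3 are not tied to milligram doses, the reader cannot tell which dose is without a Δ*. For that dose the final decision rule has no value, the planned figure has no panel, and the futility rule, which is worded over all active arms, would in effect be assessed over three.

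A SAP is meant to fix the primary model before unblinding so that nobody has to infer it. Here the governing equation disagrees with the protocol, and with the SAP's own Section 6.1, on which arms receive a primary result.

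**Working it through.** **1. Count the arms.** Protocol 9.1 plans completers of 36 (400 mg), 36 (200 mg), 36 (60 mg), 30 (20 mg), 30 (tofacitinib) and 30 (placebo).
- Total: 36 + 36 + 36 + 30 + 30 + 30 = 198, as stated, and consistent with the 6:6:6:5:5:5 ratio in Protocol 3.
- The plan's enrolment of about 230 at 15% dropout is reproduced: 198/0.85 = 232.9, or 198 × 1.15 = 227.7.
- The primary analysis excludes tofacitinib: 198 − 30 = 168, of which 138 are on PF-06650833 and 30 on placebo.

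**2. Count the model terms.**

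| | Active doses | Δ* terms | Mean parameters |
|---|---|---|---|
| Protocol 9.2 and SAP 6.1 | 4 | 4 | 6 (μ_P*, four Δ*, β) |
| SAP Appendix 4 as printed | 3 | 3 | 5 (μ_P*, three Δ*, β) |

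**3. Look for another explanation of the three.**
- *Tofacitinib.* It is excluded from this analysis. Counting it would give five active arms.
- *Text extraction.* The definition line and the summation limit both say three. The figure missing from the text near the definition would not alter the printed limit.
- *Pooling or dropping a dose.* The visible text does neither. SAP 2 says a major change to the primary analysis would also appear in a protocol amendment, and Protocol 9.2 still says four.
- *Appendix 1 of the SAP.* It names the groups only as PF-06650833 and placebo, so it does not supply the missing term.

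**4. Size of the arm left out.** If it is 20 mg: 30/168 = 17.9%. If it is 60, 200 or 400 mg: 36/168 = 21.4%.

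The SAP does not say how that arm's patients would be handled. If dropped, 168 − 30 = 138 or 168 − 36 = 132 remain. If kept, all their indicators are zero and the equation has no separate intercept, so their expected y is β(x_i^B − μ^B), which is zero change at the average baseline.

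**5. Interim futility rule.** Inputs:
- Half the planned completers: 15 (20 mg), 18, 18, 18 and 15 (placebo).
- Flat priors. The SAP specifies this type of prior for placebo at interim; flat priors for the active arms are an assumption.
- Known SD σ (assumed).

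Then P(Δ* > 0) < 0.10 is equivalent to z < −1.2816. With a shared placebo mean, the probability that every counted arm meets this is

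P = ∫ φ(u) Π_j Φ( √n_j [ u/√n_P − 1.2816 √(1/n_j + 1/n_P) − δ_j/σ ] ) du,

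where δ_j is the true effect. A single null arm gives 10%, as it should.

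All doses null (does not depend on σ):
- four arms counted: 0.01072
- 20 mg unlisted: 0.01825
- 60, 200 or 400 mg unlisted: 0.01731

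Only the unlisted dose effective, but all four arms counted (assumed effects of 4 and 8 SDAI points; assumed SD 10, 12, 15):

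| Effective dose | Effect | SD 10 | SD 12 | SD 15 |
|---|---|---|---|---|
| 20 mg | 4 | 0.00244 | 0.00342 | 0.00460 |
| 20 mg | 8 | 0.00014 | 0.00043 | 0.00111 |
| 60, 200 or 400 mg | 4 | 0.00231 | 0.00329 | 0.00451 |
| 60, 200 or 400 mg | 8 | 0.00011 | 0.00036 | 0.00100 |

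With three arms counted, the effective dose is not in the rule, so the values stay at 0.01825 or 0.01731.

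**The case against.** The strongest reply is that nobody would be misled. Protocol 9.2 describes the same model in words, with treatment as a nominal factor and four active arms. SAP 6.1 lists the four doses, and SAP 5.1 and 7 refer to any or all active arms. A change to three doses would call for an amendment that does not exist. A competent programmer would restore the missing term, no other reading is available, and no arm could be dropped in the light of results. ANCOVA and MMRM would still give an estimate for every dose (SAP 5.2.2 and 6.1.2). A key linking each d_j to a dose might also sit in part of Appendix 4 that is not visible, since the priors that SAP 6.1.2 and 7 place there are not in the public text.

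Most of this stands. The intent is clear, an error in practice is unlikely, and the interim figures are too small to carry the point. But a hidden key cannot change a summation limit of three, and the protocol's description in words does not correct the one equation to which SAP 6.1.1 sends the programmer. Needing the protocol to repair the primary model is the defect itself.

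**Conclusion.** The concern holds. As printed, the primary model gives three of the four posteriors that the protocol requires, and the decision rule has no value for one unidentified dose with 30 or 36 of 168 planned completers. This rests on counting terms and on no assumption.

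It is probably a slip of notation, but it must be corrected because it lies in the operative primary equation. For the unlisted dose, what is lost is its primary Bayesian result; its ANCOVA and MMRM estimates remain. No claim is made about the contrasts for the other three doses, which would depend on how the unlisted patients are handled and on a final placebo prior that the public text does not show.

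The interim consequence is minor and the rule is discretionary. Under the assumptions above, the chance that every counted arm meets the criterion moves from 1.07% to 1.73–1.83% if all doses are null. If only the unlisted dose works, it moves from 0.01–0.46% to 1.73–1.83%.

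**What to change.** In SAP Appendix 4, define d1 to d4 as the four randomised doses (20, 60, 200 and 400 mg), state which d_j is which dose, and change the upper limit of the sum to 4 so that Δ_1* to Δ_4* are all estimated. In SAP 7, add a sentence saying that the futility rule uses the same four-term model.

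The cost is one definition line, one summation limit and one sentence, made before the model is programmed. It needs no new data, no change in sample size and no protocol amendment, because Protocol 9.2 already specifies four active arms.
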